#### **9.7.5.2 Exploratory Endpoint Analysis**

#### **9.7.6 MTX Polyglutamate and Anti-drug Antibody Analysis**

Concentrations of pegloticase and MTX polyglutamate will be summarized by time point using descriptive statistics for the PK and mITT populations, respectively.

Incidence of anti-drug antibodies and titer levels will be summarized.

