### 3.4.3 Exploratory Endpoint Analyses

## 3.5 Analysis of Pegloticase Pharmacokinetics, Methotrexate Polyglutamates, and Anti-Drug Antibodies

### 3.5.1 Pegloticase and MTX PK

Serum samples for pegloticase PK analysis will be collected approximately 15 minutes to 2 hours after the end of infusion on Day 1; prior to infusion and approximately 15 minutes to 2 hours after the end of the infusion at Weeks 2, 6, 12 and 20. An additional PK sample will be collected at the End-of-Study (Week 24)/Early Termination Visit.

PK summaries will be done for the PK analysis set. MTX polyglutamate summaries will be done for the mITT analysis set. All results will be presented by 'as assigned' infusion duration group.

The following presentations of subject serum pegloticase concentration data covered in this SAP will be provided for pegloticase:

- A listing including subject, week/time point (actual, planned), treatment and serum concentrations. End of infusion sampling times are expressed relative to the start time of infusion.
- A table summary of serum pegloticase concentrations at each time point (n; mean, SD, coefficient of variation (CV)% calculated as  $100\% \times SD/mean$ , minimum, 25th percentile, median, 75th percentile, maximum, geometric mean and geometric CV%) will be provided for the PK analysis set. Similar tables will be produced by Month 6 sUA responder status.

Further, the mean and CV% of pegloticase concentrations will be provided by visit in the subset of subjects who are ADA positive (defined as positive for anti-PEG or anti-uricase antibodies at any visit) and ADA negative (defined as negative for both anti-PEG and anti-uricase antibodies at all visits) for each visit.

All concentrations BLQ after the first pegloticase infusion will be imputed by half of LLOQ for the analysis summaries. The number of BLQ records will be summarized. Concentrations more than 17 days after the last infusion will be excluded from the summary.

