Concentrations of MTX polyglutamate are measured for 5 active metabolites (MTX-PG1, MTX-PG2, MTX-PG3, MTX-PG4, MTX-PG5). The summary of individual 5 MTX polyglutamate values, PG1-2 (i.e., PG1 + PG2), PG3-5 (i.e., PG3 + PG4 + PG5), PG4-5 (i.e., PG4 + PG5), and total PG1-5 (i.e., PG1 + PG2 + PG3 + PG4 + PG5) over time for all mITT subjects, as well as by Month 6 sUA responders and Month 6 sUA non-responders will be provided. All concentrations BLQ are excluded from the analysis summaries. When calculating the sum over MTX-PGs, values of '<5' count as 0 in the sum.

A plot of the mean total PG1-5, and individual 5 MTX polyglutamate mean values over time will be provided for the mITT set by Month 6 sUA response status (responder vs. non-responder) for each infusion duration group.

A listing of MTX polyglutamate concentrations will be provided, showing the subject, treatment, visit, collection date and time, study day relative to first MTX treatment date, and the 5 MTX polyglutamate values along with total MTX polyglutamate values (PG1-5).

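### SAP 3.5.1 drops below-quantification MTX polyglutamate values from the single-analyte summaries but counts them as 0 in the sums, so analyte means run high, totals run low, and the two do not add up

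*SAP*

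**What the plan says.** SAP 3.5.1 plans summaries over time of the five MTX polyglutamates and of four sums (PG1-2, PG3-5, PG4-5 and PG1-5) for all mITT subjects, "as well as by Month 6 sUA responders and Month 6 sUA non-responders will be provided". It also plans a figure: "A plot of the mean total PG1-5, and individual 5 MTX polyglutamate mean values over time will be provided for the mITT set", split by Month 6 response and by infusion duration group.

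Two adjacent sentences govern low values. For the summaries: "All concentrations BLQ are excluded from the analysis summaries". For the sums: "When calculating the sum over MTX-PGs, values of '<5' count as 0 in the sum".

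For pegloticase concentrations, the same section substitutes a value instead: "All concentrations BLQ after the first pegloticase infusion will be imputed by half of LLOQ for the analysis summaries". It then adds: "The number of BLQ records will be summarized". No such count is stated for the polyglutamates.

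Protocol 9.7.6 sets no BLQ rule. It says only: "Concentrations of pegloticase and MTX polyglutamate will be summarized by time point using descriptive statistics for the PK and mITT populations, respectively".

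**The concern.** A BLQ result is a known low value, not a missing one. Leaving it out means averaging only the samples high enough to measure. Setting the same result to 0 in a sum errs the other way. The two rules appear side by side in one table and one figure, so a reader will see components that do not add to their total.

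The responder split raises the stakes a little. Subjects who meet the sUA discontinuation criterion are non-responders (SAP 3.4.2.1), and MTX stops when pegloticase stops (Protocol 9.4.3.1.1 and 9.5.2.1). Protocol 9.6.5 lists a polyglutamate sample at the End of Pegloticase Infusions Visit, and SAP Table 4 moves that sample into a scheduled visit. Lower MTX levels among non-responders are therefore plausible. They are not certain: Protocol 9.4.3.1.1 also ends pre-infusion polyglutamate sampling once infusions stop, and nothing says that such levels would reach BLQ. If they do, exclusion removes the lowest values mainly from one of the two groups being compared.

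**Working it through.** The plan gives no figure to reproduce here. The inputs from the documents are the two SAP 3.5.1 rules and the '<5' flag. Everything else below is assumed.

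**Exact result, any distribution.** Let X be the concentration of one analyte, L the limit of quantification, and f the fraction of results below L.

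- Mean reported for the analyte (BLQ excluded): E[X | X ≥ L].
- Mean contributed to the sums (BLQ = 0): (1-f) × E[X | X ≥ L].
- Ratio of the two: 1/(1-f), which is 1.05 at f = 5%, 1.11 at 10%, 1.25 at 20%, 1.43 at 30% and 2.00 at 50%.
- E[X | X ≥ L] exceeds E[X] whenever f > 0, so the analyte mean is too high. Setting BLQ to 0 makes the sums too low if the true low values are above 0.

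**Two-subject example.** Subject A has PG4 = 20 and PG5 '<5'. Subject B has PG4 = 10 and PG5 = 6. The reported means are PG4 = (20+10)/2 = 15 and PG5 = 6 (n = 1), which add to 21. The mean PG4-5 sum is (20+16)/2 = 18.

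**Size against the true mean.** Assume a lognormal concentration, L = 5 and coefficient of variation CV. Put s = √ln(1+CV²), z = Φ⁻¹(f) and μ = ln L - s·z. The true mean is M = exp(μ + s²/2). The part above L is P = M·Φ(s - z). Then excluded = P/(1-f), zero = P, and LLOQ/2 = P + f·L/2.

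Worked case, CV 80% and f = 20%: s = √ln 1.64 = 0.703, M = 11.57 and P = 10.87. Excluded is 10.87/0.8 = 13.58 at full precision (+17.4%), zero is 10.87 (-6.1%), and LLOQ/2 is 10.87 + 0.5 = 11.37 (-1.8%).

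Error over CV 50% to 120%:

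| f | BLQ excluded | BLQ = 0 | LLOQ/2 |
|---|---|---|---|
| 5% | +3.5 to +4.8% | -1.7 to -0.5% | -0.7 to -0.1% |
| 10% | +6.7 to +9.7% | -4.0 to -1.3% | -1.5 to -0.3% |
| 20% | +13.2 to +20.4% | -9.4 to -3.7% | -3.4 to -0.8% |
| 30% | +20.1 to +32.7% | -15.9 to -7.1% | -5.5 to -1.2% |
| 50% | +36.3 to +65.5% | -31.8 to -17.2% | -9.5 to -1.2% |

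**Five analytes together** (simulated, CV 80%, BLQ fractions assumed for PG1 to PG5):

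| BLQ, PG1 to PG5 | True total | Analyte means added | Mean PG1-5 with 0 |
|---|---|---|---|
| 2/2/2/5/10% | 117.45 | 121.09 (+3.1%) | 116.65 (-0.7%) |
| 5/10/5/20/50% | 74.60 | 83.02 (+11.3%) | 71.60 (-4.0%) |
| 10/20/10/40/70% | 55.17 | 66.81 (+21.1%) | 50.51 (-8.4%) |

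**Responder contrast for one analyte** (CV 80%; assumed 20% BLQ in responders and 50% in non-responders). Ratio of means:

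- true: 11.57/6.40 = 1.81
- BLQ excluded: 13.58/9.72 = 1.40
- BLQ = 0: 10.87/4.86 = 2.24
- LLOQ/2: 11.37/6.11 = 1.86

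Exclusion roughly halves the excess over 1 (0.40 against 0.81). The 0 rule widens it.

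**The case against.** The strongest reply is that little depends on these tables. MTX polyglutamates are not among the listed objectives or endpoints that can be read in either document, SAP 3.1.1 rules out inferential testing, and individual values are listed. If BLQ results are rare, the effect is small: under 5% on an analyte mean at 5% BLQ in the cases above. All of this stands, and it keeps the point minor.

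A reader might infer that exclusion removes the responder difference altogether. The documents do not support that. The same tables carry the four sums, and the figure carries PG1-5. Low-exposure subjects stay in those as 0, so the contrast is weakened only in the single-analyte rows, and only if BLQ rates differ between the groups.

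A reader might also see the pegloticase rule as a third, contradictory convention. It concerns a different drug and assay, so it need not match. The mismatch is between the two polyglutamate rules.

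Medians are already planned under SAP 3.1.1, and the n beside each mean hints at exclusions. But that n mixes BLQ with missing samples, and under exclusion the median is also taken over quantifiable values only.

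Finally, LLOQ/2 has its own cost. With '<5' read as the limit, a sample with all five analytes BLQ would total 5 × 2.5 = 12.5. Protocol 9.1 lets subjects stop MTX and remain in the study, so near-zero exposure is possible. That objection is fair, and the fix allows for it.

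**Conclusion.** The point holds as a minor flaw in a stated rule. Whenever any polyglutamate result is BLQ, the analyte means are too high, and they fail to match the sums by exactly 1/(1-f) per analyte, whatever the distribution. The downward bias in the sums also requires that the true low values are above 0. The percentage errors are illustrations that rest on an assumed lognormal shape, CV and BLQ fraction; the documents give none of these. Reading '<5' as the BLQ flag is an inference, though the natural one, because the SAP states no LLOQ for these analytes. With no BLQ results there is no effect. The consequence is confined to descriptive MTX polyglutamate tables and one plot. No primary or secondary endpoint, sample size or cohort decision is affected.

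**What to change.** Replace the two sentences in SAP 3.5.1 with one rule, for example: *MTX polyglutamate results below the LLOQ (reported as '<5') are kept in all summaries and plots and set to LLOQ/2, both for the single analytes and when forming PG1-2, PG3-5, PG4-5 and PG1-5. Samples with all five analytes BLQ are flagged. The number and percentage BLQ are shown per analyte and visit, by Month 6 responder status.* State the LLOQ explicitly.

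Any single substitution rule restores agreement: on samples with all five results, the analyte means then add exactly to the mean total. LLOQ/2 has the advantage that the section already uses it for pegloticase. The flag is needed because an all-BLQ sample would otherwise carry a total of 5 × LLOQ/2 unremarked.

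The cost is a short SAP edit, one programming rule and one extra row per table. SAP 3.1 allows this by amendment before database lock; after lock it would be documented in the study report. The downside is that means depend somewhat on the substituted value when the BLQ fraction is high, so they should be read with the planned medians. Once BLQ results are kept, a single-analyte median does not depend on the substituted value as long as fewer than half the results are BLQ.

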### 3.5.2 Anti-Drug Antibodies

Immunogenicity of pegloticase will be assessed in serum samples by evaluating anti-PEG and anti-uricase IgG antibodies. Samples will be collected prior to the pegloticase infusion on Day 1 and at the Weeks 2, 6, 12, 20 and the End-of-study (Week 24)/Early Termination Visit and 3-month Post-Treatment Follow-up Visits. In the event of an AE suspected to be an IR, a serum sample will be collected at that time or at the subsequent visit for evaluation of pegloticase/PEG antibodies.

For anti-PEG IgG antibodies, using the safety analysis set, the number and percentage of subjects who meet the following criteria will be summarized by scheduled timepoint and overall:

- ADA positive at pegloticase baseline
- ADA negative at pegloticase baseline
- ADA negative at pegloticase baseline and ADA positive at post-pegloticase baseline
  - ADA positive at pegloticase baseline with increase in titer from pegloticase baseline
  - ADA negative at pegloticase baseline and ADA positive at post-pegloticase baseline or with increase in titer from pegloticase baseline (i.e. ADA positive status post-baseline)

For anti-uricase IgG antibodies, the number and percentage of subjects with ADA positive at pegloticase baseline and post-pegloticase baseline will be summarized by scheduled timepoint.

Kaplan-Meier estimates of the time to positive anti-PEG response (for subjects who were negative at baseline) or increase in anti-PEG titer (for subjects who were positive at baseline), and the time to anti-uricase response with 25th percentile, median, 75th percentile, and 95% CI, along with a Kaplan-Meier curve will be produced. Subjects who never have a positive anti-PEG response or increase in titer will be censored at the date of their last visit (3 month follow up visit, or, if the subject did not attend this visit, then whatever last visit they have on record). Antibody result from both scheduled and unscheduled visits will be included for the time to event analysis.

Anti-PEG and anti-uricase titer will be summarized descriptively with mean and CV% by study visit. Additionally, Anti-PEG titers at the last pegloticase infusion and post-treatment will be summarized for ADA positive post-baseline subjects.

All results will be presented by ‘as assigned’ infusion duration group.

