
19. Serum samples for evaluation of anti-PEG antibodies and anti-uricase IgG antibodies will be collected prior to the infusion on Day 1 and at the Weeks 2, 6, 12, 20. An additional sample will be collected at each of the End of Study/Early Termination Visit and the 3-month Study Follow-up Visit. In the event of an AE suspected to be an IR, a serum sample will be collected in a SST tube at that time or at the subsequent visit for evaluation of anti-drug antibodies.
20. For women of childbearing potential, a serum pregnancy test will be performed at the Screening Visit; at the End-of-Study/Early Termination Visit.
21. For women of childbearing potential, a urine pregnancy test will be performed at all indicated visits and results must be confirmed by site personnel prior to any infusion starting. If the subject has not ovulated by the 30-day Follow-up email/phone call, the subject will be requested to return to the site for a urine pregnancy test.
22. Urine Albumin: Creatinine Ratio is derived data by the lab using results from urine.
23. The intent is to obtain at least 3 months of follow-up on each subject after cessation of pegloticase infusions. If the subject ends treatment early but remains in the study and the 3-month Post-Treatment Follow-up Visit occurs prior to Week 24, the 3-month Post-Treatment Follow-up Visit will be adjusted accordingly based on the timing of the last treatment. All subjects will be followed for a minimum of 3 months following Week 24/End-of-Study/Early Termination Visit.
24. Subjects who are non-vasectomized males will be asked 3 months after MTX discontinuation regarding partner pregnancy. This will occur at a regularly scheduled visit or by a separate phone/email visit.
25. Thirty (30) days after the last MTX dose, subjects will be contacted by telephone or email to review AEs and SAEs. Subjects who are females of childbearing potential will be asked to confirm that ovulation has occurred. If the subject has not ovulated, the subject will be requested to return to the site for a urine pregnancy test.

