### **9.6.4 Anti-drug Antibody Measurements**

Immunogenicity of pegloticase will be assessed via serum samples for evaluation of anti-PEG and anti-uricase IgG antibodies. Samples will be collected prior to the pegloticase infusion on Day 1 and at the Weeks 2, 6, 12, 20 and the End of study (Week 24)/Early Termination Visit and 3-month Post-Treatment Follow-up Visits. In the event of an AE suspected to be an IR, a serum sample will be collected at that time or at the subsequent visit for evaluation of pegloticase antibodies.

Each sample collection date and time will be recorded in source documents and the eCRF.

Detailed instructions regarding blood sample timing and handling are provided in the Laboratory Manual.

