## **9.6.5 MTX Polyglutamate Measurements**

Blood samples will be collected prior to pegloticase infusion on Day 1, Weeks 14, 22, End of Pegloticase Infusions Visit (if applicable) and 24 Visits during the Pegloticase + MTX Period.

Each sample collection date and time will be recorded in source documents and the eCRF.

Detailed instructions regarding blood sample timing and handling are provided in the Laboratory Manual.

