### 3.1.5 Visit Windowing

For all analyses, data will be summarized according to the scheduled visit and time points as outlined in the protocol and by the visit denoted on the electronic case report form (eCRF). The reference date associated with each visit is collected on the Visit Date eCRF page. Further, the End of Study/Early Termination (ET) visit and the End of Pegloticase Infusion Visit will be windowed to a visit based on the study day of occurrence relative to the target day of each scheduled visit according to Tables 1-8 below.

**Table 1: Visit Windows for Assigning End of Study/ET and End of Pegloticase Visits to a Scheduled Visit (Vital Signs, sUA)**

Study Period	Visit	Target Day a	Window for Reassignment to Scheduled Visit (days)
Pegloticase + MTX	Day 1	1	1
	Week 2	15	2 – 22
	Week 4	29	23 – 36
	Week 6	43	37 – 50
	Week 8	57	51 – 64
	Week 10	71	65 – 78
	Week 12	85	79 – 92
	Week 14	99	93 – 106
	Week 16	113	107 – 120
	Week 18	127	121 – 134
	Week 20	141	135 – 148
	Week 22	155	149 – 162
	Week 24	169	≥ 163

a Study days in the Pegloticase + MTX Period will be calculated relative to the first dose of Pegloticase.

**Table 2: Visit Windows for Assigning End of Study/ET and End of Pegloticase Visits to a Scheduled Visit (Laboratory Assessments and Urine Albumin: Creatinine Ratio)**

Study Period	Visit	Target Day a	Window for Reassignment to Scheduled Visit (days)
Pegloticase + MTX	Day 1	1	1
	Week 2	15	2 – 29
	Week 6	43	30 – 71
	Week 14	99	72 – 127
	Week 22	155	128 – 162
	Week 24	169	≥ 163

a Study days in the Pegloticase + MTX Period will be calculated relative to the first dose of Pegloticase.

[figure not shown]
**Table 3: Visit Windows for Assigning ET and End of Pegloticase Visits to a Scheduled Visit (Pegloticase PK and Antibody testing)**

Study Period	Visit	Target Day a	Window for Reassignment to Scheduled Visit (days)
Pegloticase + MTX	Day 1	1	1
	Week 2	15	2 – 29
	Week 6	43	30 – 64
	Week 12	85	65 – 113
	Week 20	141	114 – 155
	Week 24	169	≥ 156

a Study days in the Pegloticase + MTX Period will be calculated relative to the first dose of Pegloticase.

**Table 4: Visit Windows for Assigning ET and End of Pegloticase Visits to a Scheduled Visit (Pre-infusion MTX Polyglutamate PK)**

Study Period	Visit	Target Day a	Window for Reassignment to Scheduled Visit (days)

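### Time to antibody response is censored at the last visit of any kind rather than the last antibody sample, and the last-infusion titer has no derivation rule although most infusion visits, including Week 22, have no scheduled sample

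*SAP*

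**What the plan says.** **Sampling.** Protocol 9.6.4 takes antibody samples "prior to the pegloticase infusion on Day 1 and at the Weeks 2, 6, 12, 20 and the End of study" or early termination visit, and again at the 3-month follow-up. Footnote 19 of the Schedule of Assessments agrees: after the Week 20 sample, "An additional sample will be collected at each of the End of Study/Early Termination Visit and the 3-month Study Follow-up Visit". SAP 1.4.2 and 3.5.2 repeat the same list. A suspected infusion reaction triggers one further sample, at the time or at the next visit. None of the four places lists Week 22 or the End of Pegloticase Infusions Visit. Where the protocol wants blood at those visits it names them, as for MTX polyglutamate in 9.6.5: "Weeks 14, 22, End of Pegloticase Infusions Visit (if applicable) and 24 Visits".

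**Censoring.** In SAP 3.5.2, subjects who never have a positive anti-PEG response or a titer increase "will be censored at the date of their last visit", meaning the "3 month follow up visit, or, if the subject did not attend this visit, then whatever last visit they have on record". No censoring rule is given for time to anti-uricase response. Results from unscheduled visits do enter the analysis.

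**Last-infusion titer.** SAP 3.5.2 also states that "Anti-PEG titers at the last pegloticase infusion and post-treatment will be summarized for ADA positive post-baseline subjects". It does not say which sample supplies that titer.

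**Windowing.** SAP Table 3 in 3.1.5 is titled "Visit Windows for Assigning ET and End of Pegloticase Visits to a Scheduled Visit (Pegloticase PK and Antibody testing", so it expects antibody data from End of Pegloticase visits.

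**The concern.** An antibody response can be seen only in a sample. A subject tested negative at Week 12 and last seen at an unsampled visit at Week 20 is known to be negative up to Week 12 and no further. Censoring at Week 20 counts eight untested weeks as antibody-free. It can also keep the subject in the risk set on a date when others are tested and may convert. The denominator is then too large and cumulative incidence is pulled down.

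The titer table has a different problem. Read literally, it needs a sample at the last infusion, and completers have none scheduled. Without a rule, a programmer could use Week 20, use Week 24, or report the value as missing.

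The antibody profile is a stated exploratory objective, and the protocol's background links antibodies to loss of response and infusion reactions. These outputs should therefore mean what their titles say.

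**Working it through.** **Inputs.** Infusions on Day 1 and every two weeks to Week 22 (12 visits). Scheduled antibody samples as listed in protocol 9.6.4. Target day = 7 × week + 1. The End of Pegloticase visit is taken at its latest, 14 days after the last infusion. The 30-day contact is 30 days after it.

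**Step 1: reproduce SAP Table 3.** Midpoints between consecutive target days give (15+43)/2 = 29, (43+85)/2 = 64, (85+141)/2 = 113 and (141+169)/2 = 155. These match the upper bounds in Table 3, so the SAP's own antibody grid has no Week 22 time point.

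**Step 2: untested days, by last infusion and by last visit on record.**

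| Last infusion | Last scheduled sample at or before it | Days untested at that infusion | At End of Pegloticase visit (+14) | At 30-day contact (+30) |
|---|---|---|---|---|
| Day 1 | Day 1 | 0 | 14 | 30 |
| Week 2 | Week 2 | 0 | 14 | 30 |
| Week 4 | Week 2 | 14 | 28 | 44 |
| Week 6 | Week 6 | 0 | 14 | 30 |
| Week 8 | Week 6 | 14 | 28 | 44 |
| Week 10 | Week 6 | 28 | 42 | 58 |
| Week 12 | Week 12 | 0 | 14 | 30 |
| Week 14 | Week 12 | 14 | 28 | 44 |
| Week 16 | Week 12 | 28 | 42 | 58 |
| Week 18 | Week 12 | 42 | 56 | 72 |
| Week 20 | Week 20 | 0 | 14 | 30 |
| Week 22 | Week 20 | 14 | not applicable | 44 |

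Untested time is therefore 14 to 42 days if the last visit is an unsampled infusion visit, 14 to 56 days if it is an End of Pegloticase visit, and up to 72 days if the 30-day contact counts as a visit.

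**Step 3: last-infusion titer.** Five of the 12 infusion visits have a scheduled sample (Day 1, Weeks 2, 6, 12, 20). Seven do not (Weeks 4, 8, 10, 14, 16, 18, 22). For completers the last infusion is on day 155. The nearest samples are on day 141 (155 − 141 = 14 days before) and day 169 (169 − 155 = 14 days after).

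**Step 4: when the censoring rule moves the estimate.** A Kaplan-Meier curve changes only if the untested time reaches a date on which others have events. On target days, an unsampled infusion visit never reaches the next sampling date. An End of Pegloticase visit at +14 days reaches it after a last infusion at Day 1 (day 1 + 14 = 15), Week 4 (29 + 14 = 43), Week 10 (71 + 14 = 85) or Week 18 (127 + 14 = 141). The ±3-day visit window and unscheduled samples blur this, but the effect should be limited.

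**Step 5: illustrative size.** The documents give no expected seroconversion rate or loss pattern, so these are assumptions: 110 subjects; constant hazard −ln(1 − p)/168 per day, with p = 30% or 50% at Week 24; 10%, 20% or 30% of subjects lost, their last infusion spread evenly over Weeks 2 to 20 and their last visit an unsampled End of Pegloticase visit at +14 days; 600 runs. Mean Week 24 incidence:

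| True p | Lost | Censored at last visit | Censored at last sample | Difference (points) |
|---|---|---|---|---|
| 30% | 10% | 29.51% | 29.72% | 0.21 |
| 30% | 20% | 29.22% | 29.65% | 0.43 |
| 30% | 30% | 28.85% | 29.54% | 0.69 |
| 50% | 10% | 49.76% | 50.07% | 0.31 |
| 50% | 20% | 49.46% | 50.10% | 0.64 |
| 50% | 30% | 49.00% | 50.03% | 1.03 |

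Last-visit censoring is lower in every row. The simulation did not cover the case where the 30-day contact sets the censoring date.

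**The case against.** The strongest reply is that little turns on this. The default censoring visit, at 3 months, is sampled, and so is Week 24/early termination. For anyone whose last visit is one of these, last visit and last sample coincide. Only subjects last recorded at an unsampled visit are affected, and the simulated bias is about one point or less. The 72-day figure also needs the 30-day contact to count as a visit. Protocol 9.1 describes it as phone or email, while the synopsis section on duration of treatment calls it a visit, so this is unclear. The endpoint itself is incidence and titer, mostly summarized as counts, and no testing is planned. All of this stands. It limits the severity but does not make the rule correct.

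Table 3 does no harm by itself. It also serves early termination visits, which are sampled, and a reaction-triggered sample could fall at an End of Pegloticase visit. That stands too; what remains is a mismatch to tidy.

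Two stronger readings are tempting. A reader might infer that subjects stopped for two high sUA values have no antibody sample until Week 24, so that onset near a Week 10 stopping visit would be dated 14 weeks late. The documents do not support this as a general statement. The stopping visit may itself be a sampled week (6, 12 or 20), and a suspected reaction triggers a sample. The 3-month visit is also sampled, and protocol 9.4.3.1.1 allows that it may fall before Week 24. After a last infusion at Week 8 that would be about Week 21 (8 + 13), a lag of about 11 weeks. Footnote 23 also asks for 3 months after Week 24, so the timing is ambiguous. A reader might also infer that the last-infusion titer cannot be produced for completers. It can, from the Week 20 sample; what is missing is the rule.

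**Conclusion.** The point holds and is minor. For subjects whose last recorded visit is unsampled, the SAP counts 14 to 56 untested days as antibody-free, or up to 72 if the 30-day contact is a visit. The direction of the bias in cumulative anti-PEG incidence is downward. Its size, about 0.2 to 1.0 points at Week 24, rests on the assumed seroconversion and loss rates in Step 5, none of which is in the documents. A larger effect is possible if the 30-day contact sets many censoring dates, but that has not been sized.

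The last-infusion titer lacks a derivation rule and has no scheduled sample at 7 of 12 infusion visits, including the last infusion of every completer. The 7 of 12 counts visits, not subjects. Table 3 and protocol 9.6.4 do not agree on whether antibodies are sampled at the End of Pegloticase visit. The primary and secondary endpoint definitions do not depend on any of this.

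**What to change.** In the SAP only:

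1. Section 3.5.2: censor subjects without an event at the date of their last evaluable antibody sample, and state the same rule for time to anti-uricase response.
2. Section 3.5.2: define the last-infusion titer as the last sample at or before the last infusion, which for completers is normally Week 20, and label the table accordingly.
3. Section 3.1.5: reconcile Table 3 with protocol 9.6.4, either by dropping End of Pegloticase visits for antibody data or by saying that only triggered or unscheduled samples there will be windowed.

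These need no new data and cost only the wording and programming change. SAP 3.1 requires an SAP amendment for changes before database lock and a note in the study report for changes after it. An added antibody tube at the End of Pegloticase visit is optional. It would shorten the gap for early stoppers but would need a protocol amendment and IRB approval (protocol 9.8). The SAP changes stand without it.
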